3.8.2.2 PFS in patients with *PIK3CA* non-mutant status measured in tissue

PFS in the *PIK3CA* non-mutant cohort will be analyzed at a single look based on the FAS population according to the treatment arm patients were randomized to and the strata they were assigned to at randomization. Refer to [Section 2-2](#) for the cut-off date for efficacy.

PFS treatment effect in this cohort will be considered to be clinically relevant via a Bayesian decision rule if:

- The estimated HR (stratified according to presence of lung and/or liver metastasis and previous treatment with CDK4/6 inhibitor) ≤ 0.60

and

- The posterior probability ($HR < 1$) $\geq 90\%$

The posterior probability in the second criterion will be derived from the Bayesian posterior distribution of the HR. Assuming a non-informative prior distribution, the distribution of the HR will be updated with all available data from the patients included in the FAS in this cohort. The cumulative posterior distribution will be used to derive the probability that the true HR is less than 1.

If both these criteria are met then the comparison of PFS between the two treatment arms in this cohort using a stratified log-rank test at a one-sided 0.5% level of significance, will be made. Assuming proportional hazards model for PFS, the following statistical hypotheses will be tested at the one-sided 0.5% level of significance:

$$H_{01}: \theta_1 \geq 0 \text{ vs. } H_{a1}: \theta_1 < 0$$

where θ_1 is the log-hazard ratio (alpelisib + fulvestrant treatment arm vs. placebo+fulvestrant treatment arm) of PFS.

The median PFS along with 95% confidence intervals will be presented by treatment arm.

3.8.2.3 OS in patients with *PIK3CA* non-mutant status measured in tissue

OS analyses will be performed only if the secondary efficacy endpoint, PFS, in this cohort meets the PoC criteria given in [Section 3.8.2.2](#) and is statistically significant. A hierarchical testing procedure will be adopted. Assuming proportional hazards model for OS, the following statistical hypotheses will be tested at the one-sided 0.5% level of significance:

$$H_{01}: \theta_1 \geq 0 \text{ vs. } H_{a1}: \theta_1 < 0$$

where θ_1 is the log-hazard ratio (alpelisib + fulvestrant treatment arm vs. placebo+fulvestrant treatment arm) of OS.

The analysis for OS will be based on the FAS population according to the treatment arm patients were randomized to and the strata they were assigned to at randomization.

The final OS analysis will not be performed at the time point of the final PFS analysis in the *PIK3CA* non-mutant cohort, but after additional follow-up. Therefore, a three-look group sequential design is considered for OS, see Section 3.12.3 for further details.

OS will be estimated using the Kaplan-Meier method. The median OS along with 95% confidence intervals will be presented by treatment arm. Stratified Cox regression will be used to estimate the HR of OS, along with 95% confidence interval. The pattern of censored data will be examined between the treatment arms as described in [Section 3.8.2.1](#).

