4.3 Definition of end of the study

The end of the study for a given patient is defined as when the patient permanently discontinues study treatment with alpelisib + fulvestrant or placebo + fulvestrant and all the end of trial procedures are completed. The end of the overall study is defined as the time point when data collection will stop in both cohorts and the final analysis of the study will occur.

The primary analysis will occur when approximately the required number of PFS events is reached (refer to [Section 10.8](#)). The primary clinical study report (CSR) will be produced once the required number of PFS events is reached.

If the enrollment in the *PIK3CA* mutant cohort is stopped due to futility at the interim analysis or if the primary PFS analysis in the *PIK3CA* mutant cohort does not demonstrate a statistically significant treatment effect, then all subjects in each cohort will be followed for safety until 30 days post last dose and data collection will stop after all patients have discontinued study treatment and completed the safety follow-up period.

In the *PIK3CA* mutant cohort, if the primary endpoint of PFS is statistically significant the study will remain open, then patients still being followed, including patients in the *PIK3CA* non-mutant cohort, continue as per the schedule of assessments.

The study will end once the final OS analysis in the *PIK3CA* mutant cohort is performed approximately when the required number of deaths is observed or when statistical significance is reached for OS analysis (see [Section 10](#)) and the final analysis of study data is conducted. All available data from all patients in each cohort up to this cut-off date will be analyzed.

Patients continuing to derive benefit from study treatment in the opinion of the investigator at the end of the study will be able to continue receiving trial therapy on an individual basis (e.g. separate protocol or Novartis providing study treatment to the investigator as per local regulations).

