10.5.1 Key secondary objective(s)

The key secondary objective of the study is to determine whether treatment with alpelisib in combination with fulvestrant prolongs OS compared to treatment with placebo for the cohort of patients with *PIK3CA* mutant status.

OS is defined as the time from date of randomization to date of death due to any cause. If a patient is not known to have died, then OS will be censored at the date of last known date patient alive.

In the *PIK3CA* mutant cohort, a hierarchical testing procedure will be adopted and the OS analyses will be performed only if the primary efficacy endpoint PFS is statistically significant.

Assuming proportional hazards model for OS, the following statistical hypothesis for OS will be tested using a stratified log-rank test (according to randomization stratification factors) at the one-sided 2.0% level of significance :

$$H_0: \theta_2 \geq 0 \text{ vs. } H_a: \theta_2 < 0$$

where θ_2 is the log-hazard ratio (alpelisib-fulvestrant treatment arm vs. placebo-fulvestrant treatment arm) of OS.

The analysis for OS will be based on the FAS population according to the treatment arm patients were randomized to and the strata they were assigned to at randomization.

The final OS analysis will not be performed at the time point of the final PFS analysis in the *PIK3CA* mutant cohort, but after additional follow-up. Therefore, a three-look group sequential design is considered for OS.

OS will be hierarchically tested for the *PIK3CA* mutant cohort in the following way:

- The first potential timepoint for OS analysis will be at the time of the PFS efficacy interim analysis after approximately 37% of the expected deaths are observed, at which point approximately 66 deaths are expected. If PFS is not statistically significant at this stage, then OS will not be tested, in which case the next potential timepoint for OS analysis will be at the time of the final PFS analysis after approximately 57% of the expected deaths are observed, at which point approximately 101 deaths are expected to have been recorded in the clinical database.
- If OS is not statistically significant at the first interim analysis, the 2nd OS analysis will be planned after approximately 85% of the expected deaths are observed, at which point approximately 151 deaths have been recorded in the clinical database.

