10.5.2.2 OS in patients with *PIK3CA* non-mutant status measured in tissue

OS analyses will be performed only if the secondary efficacy endpoint, PFS, in this cohort meets the PoC criteria given in [Section 10.5.2.1](#) and is statistically significant. A hierarchical testing procedure will be adopted. Assuming proportional hazards model for OS, the following statistical hypotheses will be tested at the one-sided 0.5% level of significance:

$$H_{01}: \theta_1 \geq 0 \text{ vs. } H_{a1}: \theta_1 < 0$$

where θ_1 is the log-hazard ratio (alpelisib + fulvestrant treatment arm vs. placebo+fulvestrant treatment arm) of OS.

The analysis for OS will be based on the FAS population according to the treatment arm patients were randomized to and the strata they were assigned to at randomization.

The final OS analysis will not be performed at the time point of the final PFS analysis in the *PIK3CA* non-mutant cohort, but after additional follow-up. Therefore, a three-look group sequential design is considered for OS.

If PFS in the non-mutant cohort meets the PoC criteria and is statistically significant at a one-sided 0.5% level of significance, OS will be hierarchically tested in the following way:

- The first timepoint for OS analysis will be at the time of the final analysis for PFS (provided PFS is statistically significant) when approximately 29% of the expected deaths are observed, at which point approximately 36 deaths in the *PIK3CA* non-mutant cohort have been recorded (after approximately 18 months from the first patient to be randomized in this cohort).

- If OS is not statistically significant at the first interim analysis, the 2nd OS analysis will be planned after approximately 87% of the expected deaths are observed, at which point approximately 109 deaths are expected to have been recorded in the clinical database.
- If OS is not statistically significant at the second interim analysis, a final analysis is planned after approximately 125 deaths are expected to have been recorded in the clinical database.
- If PFS is not statistically significant, then OS will not be tested.

OS will be estimated using the Kaplan-Meier method. The median OS along with 95% confidence intervals will be presented by treatment arm. Stratified Cox regression will be used to estimate the HR of OS, along with 95% confidence interval.

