1.2 Objectives

The study objectives and corresponding endpoints as specified in the protocol are provided in [Table 1-1](#).

Table 1-1 Study objectives

Objective	Endpoint	Analysis
Primary		Refer to Section
To determine whether treatment with alpelisib in combination with fulvestrant prolongs PFS compared to treatment with placebo in combination with fulvestrant for patients with PIK3CA mutant status	PFS based on local radiology assessments and using RECIST 1.1 criteria in the PIK3CA mutant cohort	3.8.1
Key secondary		Refer to Section
To determine whether treatment with alpelisib in combination with fulvestrant	OS in the PIK3CA mutant cohort	3.8.2.1

Objective	Endpoint	Analysis
prolongs overall survival (OS) compared to treatment with placebo in combination with fulvestrant for patients with PIK3CA mutant status		
Other secondary		Refer to Section
To establish proof of concept of treatment benefit with alpelisib in combination with fulvestrant with respect to PFS for patients with PIK3CA non-mutant status	PFS based on local radiology assessments and using RECIST 1.1 criteria in the PIK3CA non-mutant cohort	3.8.2.2
To evaluate the two treatment arms with respect to OS for patients with PIK3CA non-mutant status	OS in the PIK3CA non-mutant cohort	3.8.2.3

• To evaluate the two treatment arms and cohorts of interest with respect to overall response rate (ORR), clinical benefit rate.• To evaluate the two treatment arms and cohorts of interest with respect to time to deterioration of ECOG performance status.• To evaluate the safety and tolerability of alpelisib in combination with fulvestrant	
ORR and CBR in each of the PIK3CA mutant and non-mutant cohorts
 
Time to definitive deterioration of the ECOG performance status of the score from baseline in each of the PIK3CA mutant and non-mutant cohorts
 
- Type, frequency and severity of adverse events per CTCAEv4.03- Type, frequency and severity of laboratory toxicities per CTCAEv4.03	
3.8.2.5
 
3.8.2.6
 
3.8.2.8
 
3.9

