Scenario	Look	# deaths	Simulated cumulative probabilities (%) [*]	Simulated incremental probabilities (%) [*]
			Stop for efficacy	Stop for efficacy
	2nd Interim	151	1.11	1.09
	Final OS	178	1.89	0.79
Under H_0 (HR.=0.67)	1st Interim	66	1.94	1.94
	2nd Interim	151	57.01	55.07
	Final OS	178	71.62	14.61
Scenario 2: The first IA for OS is performed at the time of the final PFS analysis				
Under H_0 (HR.=1)	1st Interim	101	0.17	0.17
	2nd Interim	151	1.12	0.95
	Final OS	178	1.91	0.79
Under H_a (HR.=0.67)	1st Interim	101	19.14	19.14
	2nd Interim	151	56.60	37.46
	Final OS	178	71.57	14.97

Note: Simulations are performed in East 6.3 with number of simulations = 10,000 and randomization seed =37059.

* Probabilities are reported as if OS was tested alone, regardless the testing strategy with PFS. The true probabilities should take into account the probability of PFS at each look. Simulated probabilities shown based on the alpha allocated for testing (p=0.02).

At the time of final PFS analysis in this cohort, both PFS and interim OS analysis will be performed by the Sponsor's clinical team. Investigators and patients will remain blinded to study treatment and all patients will continue to be followed for OS until the final OS analysis (or earlier if OS reaches statistical significance at any of the interim analyses).

3.12.3 OS in the PIK3CA non-mutant cohort:

OS will be compared between the two treatment groups, provided the PFS is statistically significant favouring alpelisib, in the *PIK3CA* non-mutant cohort. A hierarchical testing procedure will be adopted in this study and the OS analyses will be tested only if PFS is statistically significant. A maximum of three analyses are planned for OS:

- at the time of the final analysis for PFS (provided PFS is statistically significant) when approximately 29% of the expected deaths are observed, at which point approximately 36 deaths in the *PIK3CA* non-mutant cohort have been recorded (after approximately 18 months from the first patient to be randomized in this cohort);
- at the time when approximately 87% of the expected deaths are observed, at which point approximately 109 deaths in the *PIK3CA* non-mutant cohort have been recorded (after approximately 45 months from the first patient to be randomized in this cohort);
- a final analysis for OS when approximately 125 deaths in the *PIK3CA* non-mutant cohort have been recorded (approximately 54 months from date of first patient to be randomized in this cohort).

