4.7.3 Sample size considerations and simulation details

Based on the assumption that $\log(HR)$ is normally distributed, then the minimum number of events to satisfy criterion (b) can be calculated ([Schoenfeld 1981](#)) as:

$$\# \text{ events} = 4 (Z_{1-\alpha} + Z_{1-\beta})^2 / \theta^2$$

Taking, $\theta = \log(0.6)$, and one-sided, $\alpha=0.005$, $\beta=0.5$, then 102 events are required. That is, with at least 102 events if the estimated HR is < 0.6 then criterion (b) in [Section 4.7.2](#) will be met.

Assuming an enrollment rate of 10 patients during the first 6 months (7 with *PIK3CA* non-mutant status), 30 patients up to 12 months (21 with *PIK3CA* non-mutant status) and 50 patients afterwards (35 with *PIK3CA* non-mutant status) and 10% patients will be lost to follow-up, 220 patients will be randomized (110 per arm), in order to observe the required 102 events in the two arms in approximately 18 months (if the observed HR is 0.6 and the median PFS for the control arm is 7.4 months).

The primary analysis to estimate the HR will be performed after approximately 102 PFS events have been observed. If the true HR is 1, the probability (obtained by simulation) to obtain a positive conclusion is 0.005. If the true HR is 0.60 (reflecting the minimum clinically relevant difference), the probability to meet efficacy criteria is 0.491. In addition if the true HR is 0.6 and the PoC is met, the probability (by simulation) to also observe a positive result with formal testing is 0.983.

Table 4-2 Operating characteristics for PoC criteria in *PIK3CA* non-mutant cohort

True HR	True Median PFS alpelisib (months)	Probability to meet PoC	Probability formal testing is positive given PoC is met*
0.3	24.67	0.999	0.999
0.4	18.50	0.975	0.999
0.5	14.80	0.813	0.994
0.6	12.33	0.491	0.983
0.7	10.57	0.220	0.972
0.8	9.25	0.076	0.970
0.9	8.22	0.020	0.956
1.0	7.4	0.005	0.940

Assumes: (1) HR.=0.6, (2) true median PFS for fulvestrant = 7.4 months, (3) protocol planned accrual rates, (4) Analysis after 102 PFS events have been observed

* Probabilities conditional on PoC criteria being met. Formal testing using log-rank test at a one-sided, $\alpha=0.005$

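### In the non-mutant cohort the PFS gate is written on performing any OS analysis, not only on testing OS, so a listed secondary objective may end without an estimate

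*SAP*

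**What the plan says.** SAP 3.8.2.3 opens with the condition that "OS analyses will be performed only if the secondary efficacy endpoint, PFS, in this cohort meets the PoC criteria" and is statistically significant. The Kaplan-Meier, median and stratified Cox outputs for OS are specified inside that same section. Protocol 10.5.2.2 carries the same sentence, and Protocol 10.7.3 makes the performance of OS analyses depend on significant PFS.

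Other parts of the documents read differently:

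- SAP 1.2 (and Protocol Table 3-1) lists the objective without any condition: "To evaluate the two treatment arms with respect to OS for patients with" non-mutant status.
- SAP 3.12.3 says "the OS analyses will be tested only if PFS is statistically significant". SAP 1.1 likewise makes only the testing of non-mutant OS conditional, and the last bullet of Protocol 10.5.2.2 says only that OS will not be tested.
- Protocol 4.3 keeps non-mutant patients on the assessment schedule when mutant PFS is significant, and says of the end of the study: "All available data from all patients in each cohort up to this cut-off date will be analyzed".

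For the mutant cohort, Protocol 10.5.1 says "the OS analyses will be performed only if the primary efficacy endpoint PFS is statistically significant" and Protocol 10.7.2 agrees. The operative SAP sections, 3.8.2.1 and 3.12.2, say that OS will be tested under that condition.

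**The concern.** A hierarchical gate protects the type I error of a test. An estimate with a confidence interval uses no alpha and needs no gate. As SAP 3.8.2.3 is written, a shut gate removes the estimate too, and no ungated OS estimate for the tissue-defined non-mutant cohort is specified elsewhere. SAP 3.8.2.7 plans OS by ctDNA status, but in a differently defined population and under the conventions of the tissue-defined endpoint, so it is unclear whether the gate carries over.

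Two things are at stake. A listed secondary objective may be left without a curve, a median or a hazard ratio, although survival is followed. And the conflicting sections leave room to decide whether to report OS after the PFS result is known: a programmer following SAP 3.8.2.3 would produce nothing, while one following SAP 3.12.3 or Protocol 4.3 would produce estimates.

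**Working it through.** **1. Reproduce the plan's own figures.** SAP 4.7.3 uses events = 4(z₁₋α + z₁₋β)²/θ² with θ = ln 0.6, one-sided α = 0.005 and β = 0.5. This gives 4 × 2.576²/0.5108² = 101.7, and the SAP states "then 102 events are required". The figure reproduces.

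With 102 events the standard error of the log hazard ratio is 2/√102 = 0.198. A posterior probability of 90% then corresponds to an estimate of about 0.776, and one-sided p = 0.005 to about 0.600. The gate is therefore in effect an estimated PFS hazard ratio of 0.60 or less. The normal approximation Φ[(ln 0.6 − ln HR)/0.198] gives 0.821 at a true hazard ratio of 0.5 (stated 0.813), 0.500 at 0.6 (0.491), 0.218 at 0.7 (0.220) and 0.0049 at 1.0 (0.005).

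**2. Chance that the gate opens.** SAP Table 4-2 gives the probability of meeting PoC and the probability of a positive formal test given PoC. Their product is the chance that non-mutant OS is analysed under the literal rule.

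| True PFS HR | PoC met | Test positive given PoC | Gate opens | No OS estimate |
|---|---|---|---|---|
| 0.4 | 0.975 | 0.999 | 97.4% | 2.6% |
| 0.5 | 0.813 | 0.994 | 80.8% | 19.2% |
| 0.6 | 0.491 | 0.983 | 48.3% | 51.7% |
| 0.7 | 0.220 | 0.972 | 21.4% | 78.6% |
| 0.8 | 0.076 | 0.970 | 7.4% | 92.6% |
| 0.9 | 0.020 | 0.956 | 1.9% | 98.1% |
| 1.0 | 0.005 | 0.940 | 0.5% | 99.5% |

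Above 1 the table stops. The normal approximation for PoC gives about 0.1% at 1.1 and 0.01% at 1.25.

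**3. What an ungated estimate would offer.** SAP 3.15 expects about 125 deaths at about 54 months. The 95% CI factor is exp(1.96 × 2/√125) = 1.42. An estimate of 1.0 would have an interval of 0.70 to 1.42, and an estimate of 1.5 an interval of 1.06 to 2.13.

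**4. Effect on the test.** A three-look Lan-DeMets O'Brien-Fleming design at 36, 109 and 125 deaths, one-sided 0.5% and hazard ratio 0.67, gives 36.1% power, as stated in SAP 3.15. Descriptive reporting changes neither this power nor the 0.5% level.

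**The case against.** Three stronger readings are tempting, and the documents do not support them.

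*That a survival disadvantage would go unseen.* Protocol 10.5.3.2 and SAP 3.9.1.4 summarise all deaths, on and after treatment. SAP 3.9 presents safety outputs by arm for each cohort, and none of this is gated. The DMC receives safety data by cohort about every six months (SAP 2.2). Death counts would be visible. However, they are counts in the Safety Set that ignore follow-up time and censoring, so they do not replace a time-to-event estimate in the Full Analysis Set.

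*That the objective usually goes without an estimate.* This depends on the true effect. At the planned hazard ratio of 0.6 it is close to an even chance, and at 0.5 or better the gate opens at least 81% of the time. It is the usual outcome only if the effect is weaker than planned.

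*That mutant-cohort OS would be suppressed in the same way.* Only the Protocol wording points there, because SAP 3.8.2.1 and 3.12.2 already speak of testing. Moreover, if mutant PFS fails, Protocol 4.3 reduces follow-up in both cohorts to 30 days after the last dose, so later deaths would largely not be collected.

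It can also be said that the whole matter is loose wording of an ordinary hierarchical test: several passages gate only the test, and the introductions to the secondary analyses cover each cohort where appropriate. That is a fair reading of intent. But the section that defines the non-mutant OS outputs says otherwise, and nothing states which passage prevails.

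A last objection concerns the remedy. Reporting hazard ratios at every OS cut-off could release a result on about 36 non-mutant deaths or about 66 mutant deaths. SAP 3.12.3 keeps the sponsor's team blinded until the mutant cohort can be unblinded. This stands, and it limits what should be proposed.

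**Conclusion.** The point holds as a conflict over what is gated. SAP 3.8.2.3 and Protocol 10.5.2.2 and 10.7.3 gate the performance of any non-mutant OS analysis, against SAP 1.1 and 3.12.3, Protocol 4.3 and the unconditional objective. Followed literally, they leave OS unestimated in about 19% of trials at a true PFS hazard ratio of 0.5, 52% at 0.6, 79% at 0.7 and over 99% at 1.0. These figures rest on the SAP's simulations with 102 PFS events. What would be lost is the time-to-event estimate, not all sight of deaths.

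The gain from reporting it is real but modest: even with 125 deaths, an estimate of 1.0 leaves hazard ratios up to 1.42 within the interval. The 125 deaths assume that mutant PFS succeeds and follow-up runs to about 54 months. If the study ended at the second OS look, about 109 deaths would give a factor of exp(1.96 × 2/√109) = 1.46. If mutant PFS failed, follow-up would shrink and the estimate would rest on fewer deaths still. The point should be corrected because the change is cheap and a listed objective is involved; it does not threaten the primary analysis.

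**What to change.** In SAP 3.8.2.3 and Protocol 10.5.2.2 and 10.7.3, make the condition apply to formal testing of OS instead of to performing OS analyses. Make the same change in Protocol 10.5.1 and 10.7.2, to agree with SAP 3.8.2.1 and 3.12.2.

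Then add a sentence such as: *If the gate is not passed, Kaplan-Meier curves, medians and the stratified hazard ratio with 95% confidence interval for OS will be reported descriptively, without a p-value, at the final OS or end-of-study cut-off only and after the mutant cohort has been unblinded.* Say also that the number of deaths behind the estimate will be given, since it depends on how long follow-up continued.

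The cost is wording in both documents and a few outputs. No alpha, patients or visits are added. Limiting release to the final cut-off keeps the interim blinding arrangements as they are.
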